Arm A (APR-246). Patients will receive a fixed dose of 4.5 g APR-246 (1.5 g of the dose during first 45 minutes followed by 3 g of the dose during 5 hours 15 minutes) on Days 1 to 4, with carboplatin AUC 5 and PLD 30 mg/m² administered concurrently on Day 4 (treatment repeated every 28 days for up to six cycles).

Arm B (Control). Carboplatin AUC 5 and PLD 30 mg/m² administered on Day 1 of each 28-day cycle, repeated for up to six cycles.

Number of patients:

The trial will enroll up to a maximum of 400 patients with positive IHC staining for p53.

Diagnosis and main criteria for inclusion:

Inclusion criteria:

1. Archived sections from the original FFPE sample reviewed by a gynecological pathologist confirming High Grade Serous Ovarian Cancer, High Grade Serous Peritoneal Cancer or Primary Fallopian Tube Cancer, and positive IHC staining for p53 assessed according to defined standard (as detailed in the laboratory manual). Cases that do not show p53 staining will not be included.
2. Radiologically-confirmed Disease Progression between six and twenty-four (6-24) months after a first or second platinum based regimen.
3. At least a single (RECIST v1.1) measurable lesion.
4. Adequate organ function prior to registration:
 - a) Bone Marrow Reserve:
 - Absolute neutrophil count (ANC) $\geq 1.5 \times 10^9/L$,
 - Platelets $\geq 100 \times 10^9/L$,
 - Hemoglobin $\geq 9 \text{ g/dL}$.
 - b) Hepatic:
 - Total bilirubin level $< 1.5 \times \text{ULN}$,
 - ALT and AST $< 2.5 \times \text{ULN}$.
 - c) Renal:
 - Calculated creatinine clearance $> 30 \text{ mL/min}$.
 - d) Electrolytes
 - Potassium within institutional normal ranges.

5. Toxicities from previous cancer therapies, excluding alopecia, must have recovered to grade 1 (defined by CTCAE version 4.0). Chronic stable grade 2 peripheral neuropathy secondary to neurotoxicity from prior therapies may be considered on a case by case basis by the Principal Investigator.
6. If of childbearing potential, negative pre-treatment serum pregnancy test.
7. If of childbearing potential, willing to use an effective form of contraception (see below) during chemotherapy treatment and for at least six months thereafter.
Such methods include: (if using hormonal contraception this method must be supplemented with a barrier method, preferably male condom).
 - Combined (estrogen and progestogen containing) hormonal contraception associated with inhibition of ovulation:
 - Oral
 - Intravaginal
 - Transdermal

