6.5.2.1 Hematological Toxicity and Dose Modifications

The absolute neutrophil count (ANC) must be $\geq 1.50 \times 10^9/L$ and the platelet count must be $\geq 100 \times 10^9/L$ in order to administer full doses of carboplatin and PLD in each cycle as assessed on day 1. In the event of an $ANC < 1.0 \times 10^9/L$, hematological assessment should be performed twice a week until recovery of ANC to $> 1.0 \times 10^9/L$. Patients should be monitored prior to each dose for platelet and neutrophil counts, and at the discretion of the Investigator, if necessary, the dose of carboplatin and/or PLD may be either reduced or withheld in the presence of hematological toxicity according to the following scale (Table 3):

Table 3. Dose Modification of Systemic Chemotherapy for Hematological Toxicities

Hematological Assessment on Day 1 of a Cycle:			
ANC ($\times 10^9/L$)		Platelet Count ($\times 10^9/L$)	Dose Modification
≥ 1.5	and	≥ 100	Administer full dose of Carboplatin and PLD
< 1.5	and/or	< 100	Delay cycle for 7 days. If within normal acceptable parameters (as above) proceed with dose reductions of carboplatin to AUC 4 and PLD 25 mg/m ² .
Dose reduction to carboplatin AUC 4 and PLD 25 mg/m ² is also required in the following circumstances:			

• $ANC < 0.5 \times 10^9/L$ for > 7 days• An episode of febrile neutropenia (temp $\geq 38.5^\circ C$ and $ANC < 1.0 \times 10^9/L$)• Platelets $< 25 \times 10^9/L$, or bleeding requiring a platelet transfusion			

Growth factors:

- For patients who have a prolonged neutropenia, Investigators may administer growth factors to aid white cell count recovery. This should be given per the package insert.
- Patients who the Investigator considers to be at risk for developing neutropenia (considering bone marrow tolerance with prior chemotherapy or neutropenia while on the PiSARRO study)

that could affect their ability to receive study treatment per the study protocol, should consider administering prophylactic growth factor per the package insert.

For patients in Arm A:

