- If hematological recovery is inadequate by Day 42 of any cycle, the Investigator should discuss appropriate patient management with the Sponsor before allowing the patient to continue with study drug treatment. If the patient is showing signs of response, the Investigator may retain the patient in the study, but should assess the potential for further prolonged periods of marrow suppression and the associated adverse events as part of this decision process.
- In the event that a patient requires a second dose reduction of systemic chemotherapy or the initial recovery of hematologic parameters took longer than 14 days even with growth factor support, the Investigator may also consider a single level reduction in the dose of APR-246 in conjunction with a further dose reduction of chemotherapy per Table 4.

Table 4. Dose Modification of Systemic Chemotherapy for Hematological Toxicities in Arm A

Chemotherapy Modification	Treatment Delay	APR-246 Dose Modification
Initial Dose Reduction	Less than 14 days	None
	14 days or more	Reduce one level
Second Dose Reduction	Any	Reduce one level

For patients in Arm B:

- If hematological recovery is inadequate by Day 42 of any cycle after cycle 2, the Investigator should discuss appropriate patient management with the Sponsor.

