6.5.2.2.3 Cutaneous Toxicity (Palmar-Plantar Erythrodysesthesia (PPE))

Treat symptoms accordingly. Follow dosing guideline as per Table 6.

Table 6. Dose Modification of PLD for Cutaneous Toxicity

	Time after prior PLD Dose		
Toxicity Grade at Current Assessment	After Day 28 (week 4)	Days 35 and 42 (week 5)	> Day 42 (week 6)
Grade 1	Redose unless patient has experienced a previous Grade 3 or 4 skin toxicity, in which case wait an additional week	Redose unless patient has experienced a previous Grade 3 or 4 skin toxicity, in which case wait an additional week	Decrease dose by 25 %; return to 4 week interval
Grade 2	Wait an additional week	Wait an additional week	Decrease dose by 25 %; return to 4 week interval
Grade 3	Wait an additional week	Wait an additional week	Stop PLD
Grade 4	Wait an additional week	Wait an additional week	Stop PLD

Grade 1 - mild erythema, swelling, or desquamation not interfering with daily activities

Grade 2 - erythema, desquamation, or swelling interfering with, but not precluding normal physical activities; small blisters or ulcerations less than 2 cm in diameter

Grade 3 - blistering, ulceration, or swelling interfering with walking or normal daily activities; cannot wear regular clothing

Grade 4 - diffuse or local process causing infectious complications, or a bedridden state or hospitalization

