6.5.2.2.5 Other Grade 3 or 4 Non-hematological toxicities

Table 8. Other Grade 3 or 4 Non-hematological Toxicities

Grade 3 toxicity (except nausea & vomiting)	Reduce dose of PLD to 20 mg/m ² and/or reduce dose of carboplatin to AUC 4 provided toxicity has resolved to \leq Grade 1. If further toxicity occurs, an additional reduction may be made after discussion with Sponsor
Grade 4 toxicity (except nausea & vomiting)	Withhold treatment and discuss with Sponsor

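### Table 3 states chemotherapy doses as fixed values that ignore earlier reductions, so it conflicts with Tables 4 to 8, and the further reduction it calls for has no stated dose

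*Combined protocol and SAP*

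**What the plan says.** Both arms start at "carboplatin AUC 5 and PLD 30" mg/m² (Synopsis; Sections 6.4.1 and 6.4.2). Section 6.5.2 says the modifications that follow, hematological and non-hematological, are to be applied. It does not rank them.

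Table 3 (Section 6.5.2.1) has two rows keyed to Day 1 counts:

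- ANC at least 1.5 and platelets at least 100 (×10⁹/L): "Administer full dose of Carboplatin and PLD".
- Either count lower: delay 7 days and, once counts are acceptable, "proceed with dose reductions of carboplatin to AUC 4 and PLD 25" mg/m².

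The table adds that the same reduced doses apply, in that a reduction "is also required in the following circumstances": ANC below 0.5 for more than 7 days, febrile neutropenia, and platelets below 25 or bleeding that needs a platelet transfusion. The lead-in says that "at the discretion of the Investigator, if necessary, the dose of carboplatin and/or PLD may be either reduced or withheld" on the Table 3 scale.

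For Arm A, the same section allows an APR-246 reduction "in conjunction with a further dose reduction of chemotherapy per Table 4". Table 4 distinguishes an initial from a second chemotherapy reduction, but its only dose column is for APR-246. The Arm B bullet covers only inadequate recovery by Day 42.

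The other tables set PLD by different scales:

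- Table 5 (hepatic): 75% or 50%, with a stepwise return to full dose if tolerated.
- Tables 6 and 7 (skin, stomatitis): "Decrease dose by 25 %; return to 4 week interval", or stop PLD.
- Table 8 (other Grade 3): "Reduce dose of PLD to 20" mg/m² and/or carboplatin AUC 4, with a possible additional reduction after discussion with the Sponsor.

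**The concern.** Table 3 gives destinations, not steps. A fixed dose works as a reduction only for a patient who is still on the starting dose. For anyone already reduced, the same instruction can leave the dose unchanged or name a higher one. Nothing says which table prevails, and nothing says whether a reduction under Tables 3, 6, 7 or 8 is kept in later cycles.

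Two things are at stake. The first is patient safety: an instruction labeled as a reduction, or as routine full dosing, can name a dose above one set because of toxicity. The second is consistency of the chemotherapy backbone. The treatment is unblinded (Section 4.4), and the primary PFS comparison is meant to isolate APR-246. If the text leaves the post-toxicity backbone dose open, it may vary by site. Section 2.7.1 lists neutropenia and thrombocytopenia among the commonest Phase Ib adverse events, so the hematological rules are likely to be used.

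**Working it through.** There is no figure in the plan to reproduce. The check converts each reduced level to a dose and compares it with Table 3's two outputs.

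**Inputs.** Start: AUC 5, PLD 30 (Sections 6.4.1, 6.4.2). Table 3 outputs: full dose, or AUC 4 / PLD 25. Full dose is taken as the starting dose; the footnote to Table 5 uses the term in that sense.

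**Reduced PLD levels (mg/m²).**

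- Table 5: 30 × 0.75 = 22.5; 30 × 0.50 = 15.
- Tables 6 and 7: 30 × 0.75 = 22.5 from the starting dose; 25 × 0.75 = 18.75 if taken from the Table 3 level.
- Table 8: 20.

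**Change = Table 3 dose ÷ current dose − 1.**

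| Current PLD | Source | Row 1 (30) | Row 2 or further triggers (25) |
|---|---|---|---|
| 25 | Table 3 | +20.0% | 0% |
| 22.5 | Tables 5, 6, 7 | +33.3% | +11.1% |
| 20 | Table 8 | +50.0% | +25.0% |
| 18.75 | Tables 6, 7 after Table 3 | +60.0% | +33.3% |
| 15 | Table 5 | +100.0% | +66.7% |

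Carboplatin: row 1 takes AUC 4 to AUC 5, 5 ÷ 4 − 1 = +25%. Row 2 leaves AUC 4 at AUC 4, so it never raises carboplatin.

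**Passages side by side.**

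1. *Row 1 against Table 4.* A patient at AUC 4 / PLD 25 with adequate counts in the next cycle meets row 1 and is directed to full dose. Table 4's initial and second reductions make sense only if the first is carried forward.
2. *Row 2 against Tables 5 to 8.* The reduced PLD dose of 25 exceeds every reduced level those tables produce.
3. *Repeat hematological event.* At AUC 4 / PLD 25, Table 3 returns the same pair of doses. The text refers the further reduction to Table 4, which has no carboplatin or PLD entry. Table 8's additional reduction has no stated dose either.
4. *Row 1 against Table 5.* Table 5 itself allows a return to full dose. From 15 it goes to 22.5 first, whereas Table 3 names 30 or 25. The conflict is over steps and conditions, not over re-escalation as such.

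**The case against.** The best defense is that no sensible investigator would raise a dose under a rule about reductions. The lead-in speaks only of reducing or withholding, row 2 is worded as a reduction, and Section 6.5.2 applies all the tables, so a site can keep the lower dose. The text before Table 3 makes adequate counts a necessary condition for full dose, which is weaker than an instruction to give it. Only Table 5 sets out a return path, which suggests that other reductions are meant to last. Several provisions also call for discussion with the Sponsor.

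Much of this stands: keeping the lower dose is a reasonable reading. But the plan does not state it. The discretion is tied to the same Table 3 scale, and row 1 turns the necessary condition into an instruction. The missing dose behind the Table 4 reference cannot be resolved by interpretation.

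Some stronger inferences are not supported:

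- A reader might infer that Table 3 works from Day 1 counts alone. It does not; three further triggers lead to the same reduced doses.
- A reader might infer that only Arm A can have a second step-down. For hematological toxicity, a second reduction is mentioned only under Arm A, in text about when to reduce APR-246 as well, and the Arm B text is silent. That is a gap, not a stated difference, and Table 8's additional reduction is not limited to one arm.
- A reader might infer that every patient with a second dose-modifying toxicity is affected. Tables 6 and 7 use relative cuts or stop PLD, so a repeat event there has a defined result.

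**Conclusion.** The concern holds as a conflict between dose instructions and a cross-reference that leads to no dose. Read literally, Table 3 moves a patient from AUC 4 / PLD 25 back to full dose (carboplatin +25%, PLD +20%). Its reduced PLD dose is 11%, 25% or 67% above levels of 22.5, 20 or 15 mg/m² reached under Tables 5 to 8. A second hematological reduction is named but has no chemotherapy dose.

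These sizes assume that full dose means the starting dose and, for the 22.5 from Tables 6 and 7, that the 25% cut is taken from 30. They describe what the text directs, not what sites will do. The documents give no frequency for such cases. A reader might go on to infer a biased PFS comparison or a loss of power, but nothing in the plan allows that to be calculated, and no effect on power or Type I error is claimed.

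**What to change.** The sponsor should reconcile Section 6.5.2.1 (Tables 3 and 4 and the arm-specific bullets) with Sections 6.5.2.2.2 to 6.5.2.2.5 (Tables 5 to 8), so that the text states:

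- which instruction governs when two apply and differ;
- whether a reduction under Tables 3, 6, 7 or 8 persists into later cycles, and how Table 3 relates to the stepwise return in Table 5;
- what the second or further chemotherapy reduction refers to, given that Table 4 holds no carboplatin or PLD dose;
- whether that reduction applies in both arms.

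The content of these rules and the dose levels are for the sponsor to set; none is proposed here. The cost is a protocol amendment and site retraining, with no extra patients or procedures.

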6.5.2.2 Non-Hematological Toxicity

Please see relevant sections below for specific management.

Patients unable to be dosed within 4 weeks of scheduled therapy should be discussed with the Sponsor to decide if to still proceed in the study.

6.5.2.2.1 Renal Impairment

The carboplatin dose should be calculated based on GFR. If renal function drops less than 20 mL/min, the patient should be discontinued from treatment with carboplatin.

Dose modifications should not be required for PLD in patients with renal impairment.

6.5.2.2.2 Hepatic impairment

PLD can be administered to patients with liver metastases with concurrent elevation of bilirubin and liver enzymes up to 4 x the upper limit of the normal range. See Table 5 below.

Carboplatin: Transient increases in liver enzymes have been seen although no dose reduction is usually required. In severe hepatic dysfunction consider a dose reduction after discussing with the Sponsor.

Table 5. Dose Modification of PLD for Hepatic Impairment

Total bilirubin (mg/dL)	Total bilirubin (μmol/L)	PLD Dose
< 1.2	<20.52	100%
1.2 - 3.0	20.52 – 51.3	75%*
>3.0	> 51.3	50%*

*If the patient tolerates the first dose without an increase in serum bilirubin or liver enzymes, the dose for the next cycle can be increased to the next dose level, i.e., if reduced by 25% for the first dose, increase to full dose for cycle 2; if reduced by 50% for the first dose, increase to 75% of full dose for cycle 2. The dosage can be increased to full dose for subsequent cycles if tolerated.

6.5.2.2.3 Cutaneous Toxicity (Palmar-Plantar Erythrodysesthesia (PPE))

Treat symptoms accordingly. Follow dosing guideline as per Table 6.

Table 6. Dose Modification of PLD for Cutaneous Toxicity

	Time after prior PLD Dose		
Toxicity Grade at Current Assessment	After Day 28 (week 4)	Days 35 and 42 (week 5)	> Day 42 (week 6)
Grade 1	Redose unless patient has experienced a previous Grade 3 or 4 skin toxicity, in which case wait an additional week	Redose unless patient has experienced a previous Grade 3 or 4 skin toxicity, in which case wait an additional week	Decrease dose by 25 %; return to 4 week interval
Grade 2	Wait an additional week	Wait an additional week	Decrease dose by 25 %; return to 4 week interval
Grade 3	Wait an additional week	Wait an additional week	Stop PLD
Grade 4	Wait an additional week	Wait an additional week	Stop PLD

Grade 1 - mild erythema, swelling, or desquamation not interfering with daily activities

Grade 2 - erythema, desquamation, or swelling interfering with, but not precluding normal physical activities; small blisters or ulcerations less than 2 cm in diameter

Grade 3 - blistering, ulceration, or swelling interfering with walking or normal daily activities; cannot wear regular clothing

Grade 4 - diffuse or local process causing infectious complications, or a bedridden state or hospitalization

6.5.2.2.4 Stomatitis

Refer to Table 7. If delay has been necessary due to stomatitis, a change of cycle interval to five weeks is allowed if the Investigator judges it to be in the patient's best interests.

Table 7. Dose Modification of PLD for Stomatitis

		Time after prior PLD Dose		
Toxicity Grade at Current Assessment	After Day 28 (week 4)	Days 35 and 42 (week 5)	> Day 42 (week 6)	
Grade 1	Redose unless patient has experienced a previous Grade 3 or 4 stomatitis in which case wait an additional week	Redose unless patient has experienced a previous Grade 3 or 4 stomatitis in which case wait an additional week		Decrease dose by 25 %; return to 4 week interval
Grade 2	Wait an additional week	Wait an additional week		Decrease dose by 25 %; return to 4 week interval
Grade 3	Wait an additional week	Wait an additional week		Stop PLD
Grade 4	Wait an additional week	Wait an additional week		Stop PLD

Grade 1 - painless ulcers, erythema, or mild soreness**Grade 2** - painful erythema, edema, or ulcers, but can eat**Grade 3** - painful erythema, edema, or ulcers, but cannot eat**Grade 4** - requires parenteral or enteral support

6.5.2.2.5 Other Grade 3 or 4 Non-hematological toxicities

Table 8. Other Grade 3 or 4 Non-hematological Toxicities

Grade 3 toxicity (except nausea & vomiting)	Reduce dose of PLD to 20 mg/m ² and/or reduce dose of carboplatin to AUC 4 provided toxicity has resolved to \leq Grade 1. If further toxicity occurs, an additional reduction may be made after discussion with Sponsor
Grade 4 toxicity (except nausea & vomiting)	Withhold treatment and discuss with Sponsor

6.5.3 Hypersensitivity / Adverse Drug Reactions to Chemotherapy Agents

All patients will be carefully monitored for clinical features of hypersensitivity reactions. Should a hypersensitivity reaction to carboplatin occur during infusion, this must be discontinued and an attempt at desensitization may be made subsequently if deemed appropriate by the Investigator in discussion with the patient. The timing of this will be at the discretion of the Investigator depending on the initial dose of carboplatin received.

Desensitization should be performed according to local practices and monitoring.

The desensitization procedure should take place with resuscitation facilities within easy access with regular observations and a trained nurse present throughout administration of APR-246 and chemotherapy. If at any point during the dose escalation allergic signs or symptoms are apparent, the carboplatin infusion must be discontinued.

All subsequent cycles should then be given using this procedure.

If it is not possible for the patient to continue to receive carboplatin due to unmanageable hypersensitivity, the Investigator in consultation with the Sponsor can consider either to remove the patient from the study or change to cisplatin monotherapy. Cisplatin monotherapy will be administered in place of the combination chemotherapy on day 4 of all remaining treatment cycles, up to a maximum of 6 cycles (including prior combination chemotherapy).

The cisplatin monotherapy should be administered, monitored and modified according to the local practices at the investigational site.

6.5.4 Cardiac Safety Monitoring in relation to Treatment with PLD

Whenever cardiomyopathy is suspected, i.e., the left ventricular ejection fraction (LVEF) has substantially decreased relative to pre-treatment values and/or LVEF is lower than a prognostically relevant value (e.g., < 45%), the benefit of continued therapy must be carefully evaluated against the risk of developing irreversible cardiac damage. Cardiology consultation is recommended.

6.5.5 Action to be taken in the Event of QT/QTc Prolongation

Although the risk of QT/QTc prolongation is considered to be very low, in the event of prolongation of the QT/QTc interval > 500 msec or an increase of > 60 msec over baseline, study treatment should be discontinued and appropriate close (continuous) ECG monitoring in a hospital setting should be initiated until the opinion of a cardiologist is obtained.

6.6 Concomitant Treatment and Prohibited Medication

Patients are allowed to receive supportive care therapies (including cytokine, growth factors) concomitantly during the trial.

No anti-cancer therapy other than that given in this clinical trial; no immunotherapy; no hormonal cancer therapy; no radiation therapy (except palliative); and no experimental medications are permitted during the trial. All alternative therapies must first be approved by the Sponsor.

No poly (adenosine diphosphate [ADP]) ribose polymerase inhibitors are permitted until progression of disease (PD).

Concomitant use of paracetamol (acetaminophen) based compounds is allowed. However, caution should be taken when co-administrating APR-246 with high doses of paracetamol (i.e. 4 g/24 hrs). Use of paracetamol must be terminated if any liver function tests increase above normal ranges is detected.

Any disease progression that requires other specific antitumor therapy will be cause for discontinuation from the trial.

Antioxidants: Concomitant intake of acetylcysteine or other antioxidants might have a negative effect on the treatment efficacy and is therefore not recommended.

Anticoagulant therapy: Patients who are taking warfarin may participate in this trial; however, it is recommended that prothrombin time (INR and APTT) be monitored carefully at least once per week for the first month, then monthly if the INR is stable. Subcutaneous heparin is permitted.

Concurrent or procedural medications or therapy given to or taken by the patient will be recorded in the CRF along with the indication. All concomitant medications should be recorded for up to 30 days following the last protocol treatment. After this period, only relevant medication (e.g. medication in patients with treatment related AEs) will be recorded in the CRF.

Both generic and trade names may be recorded. However, the generic name is generally preferred because of its specificity, whereas trade names are preferred for combination products.

The potential interaction of APR-246 with other medicinal products has not been investigated.

